#### **4.4 CONCOMITANT THERAPY**

Concomitant therapy consists of any medication (e.g., prescription drugs, over-the-counter drugs, vaccines, herbal or homeopathic remedies, nutritional supplements) used by a patient in addition to protocol-mandated treatment from the start of the screening period to the study completion or discontinuation visit. All such medications should be reported to the investigator and recorded on the Concomitant Medication eCRF.

Patients requiring a prohibited therapy (refer to Section 4.4.1 [Table 2] and Section 4.4.2.2) will be discontinued from study treatment (see Section 4.6.1) and will undergo follow-up assessments as described in Appendix 1 and Appendix 2.

##### **4.4.1 Permitted and Prohibited Therapy for Ulcerative Colitis (Including Background and Rescue Therapy)**

Permitted and prohibited concomitant therapies for UC, including background and rescue therapies, are outlined in Table 2.

**Table 2 Permitted and Prohibited Therapies for Ulcerative Colitis**

Therapy	Prior to Screening Endoscopy a	During Screening and Induction	During Optional ATE and Safety Follow-Up	Rescue Therapy
Anti-Inflammatories				
Topical (rectal) 5-ASA	
 
Must not have received topical (rectal) 5-ASA within 2 weeks prior to screening endoscopy
 
	
 
Treatment with topical (rectal) 5-ASA is prohibited
 
	
 
Intermittent use of topical (rectal) 5-ASA is permitted up to 2 weeks of daily use; must be discontinued by [REDACTED]
 
	
 
Initiation of topical (rectal) 5-ASA is considered rescue therapy and is permitted only during the optional ATE period
 

Oral 5-ASA	
 
May be receiving oral 5-ASA if dose has been stable for at least 2 weeks prior to screening endoscopy
 
	
 
Baseline level of oral 5-ASA must be maintained
 
Initiation or increase in dose of oral 5-ASA is prohibited
 
	
 
For patients on oral 5-ASA at baseline, the dose may be tapered until discontinuation, starting at [REDACTED]
 
Initiation or increase in dose of oral 5-ASA is prohibited
 
	
 
Initiation of oral 5-ASA or increase in dose of oral 5-ASA compared with baseline is considered rescue therapy and is prohibited
 

IV corticosteroids and rectal corticosteroids (i.e., enemas or suppositories)	
 
Must not have received IV corticosteroids within 2 weeks prior to screening endoscopy
 
Must not have received rectal corticosteroids within 2 weeks prior to screening endoscopy
 
	
 
Treatment with IV or rectal corticosteroids is prohibited
 
	
 
Treatment with IV or rectal corticosteroids is prohibited
 
	
 
Initiation of IV or rectal corticosteroids is considered rescue therapy and is prohibited
 

5-ASA=5-aminosalicylic acid; ATE=active treatment extension.

a See inclusion and exclusion criteria in Section 4.1.1 and Section 4.1.2 for additional details.

**Table 2 Permitted and Prohibited Therapies for Ulcerative Colitis (cont.)**

Therapy	Prior to Screening Endoscopy a	During Screening and Induction	During Optional ATE and Safety Follow-Up	Rescue Therapy
Anti-Inflammatories (cont.)				
Oral corticosteroids	
 
May be receiving oral corticosteroids at doses ≤20 mg/day prednisone (or equivalent) if dose has been stable for at least 2 weeks prior to screening endoscopy (baseline steroid level)b, c
 
	
 
Baseline level of oral corticosteroids must be maintained (≤20 mg/day prednisone or equivalent)
 
Initiation or increase in dose of oral corticosteroids is prohibited
 
	
 
For patients on oral corticosteroids at baseline, corticosteroid dose may be tapered until discontinuation, starting at [REDACTED]
 
For patients who cannot tolerate the corticosteroid taper without recurrence of UC symptoms or experience symptoms of corticosteroid withdrawal, the corticosteroid dose can be increasedd
 
Initiation or increase in dose of oral corticosteroids above baseline steroid level is prohibited
 
	
 
Initiation of oral corticosteroids or increase in dose of oral corticosteroids above baseline steroid level is considered rescue therapy and is prohibited
 

Immunosuppressants				
AZA, 6-MP, or MTX	
 
May be receiving AZA, 6-MP, or MTX if the dose has been stable for at least 12 weeks prior to screening endoscopy
 
Discontinuation of AZA, 6-MP, or MTX must be for at least 2 weeks prior to screening endoscopy
 
	
 
Baseline level of AZA, 6-MP, or MTX must be maintained
 
Initiation or increase in dose of AZA, 6-MP, or MTX is prohibited
 
	
 
For patients on AZA, 6-MP, or MTX at baseline, the dose may be tapered until discontinuation, starting at [REDACTED]
 
Initiation or increase in dose of AZA, 6-MP, or MTX is prohibited
 
	
 
Initiation or increase in dose of AZA, 6-MP, or MTX is considered rescue therapy and is prohibited
 

6-MP=6-mercaptopurine; ATE=active treatment extension; AZA=azathioprine; MTX=methotrexate.

a See inclusion and exclusion criteria in Section 4.1.1 and Section 4.1.2 for additional details.

b The equivalent dose of budesonide to prednisone has not been fully characterized; however, ≤6 mg/day budesonide is permitted .

c There is limited/no data on beclomethasone dipropionate equivalency in inflammatory bowel disease. Beclomethasone dipropionate should not be used for more than 4 weeks based on the Clipper Summary of Product Characteristics.

d If the corticosteroid dose has not been increased above the baseline level, these patients can re-initiate corticosteroid dose tapering. Treatment with corticosteroids above the baseline dose will be considered rescue therapy.

**Table 2 Permitted and Prohibited Therapies for Ulcerative Colitis (cont.)**

Therapy	Prior to Screening Endoscopy a	During Screening and Induction	During Optional ATE and Safety Follow-Up	Rescue Therapy
Advanced Therapies				
Biologics: 
 
• Anti-TNFs
 
• Anti-integrin
 
• Anti-interleukins
 
 Small molecules: 
 
• S1P receptor modulators
 
	
 
• Must not have received an advanced therapy within 8 weeks for biologic therapy, 2 weeks for non-biologic therapy, or 5-half-lives prior to screening endoscopy, whichever is longer
 
	
 
• Treatment with advanced therapy is prohibited
 
	
 
• Treatment with advanced therapy is prohibited
 
	
 
• Advanced therapies are prohibited as rescue therapy
 

JAK inhibitors	
 
• Inadequate response or loss of response to prior treatment with JAK inhibitor is exclusionary
 
• Discontinuation of JAK inhibitor must be for at least 2 weeks prior to screening endoscopy
 
	
 
• Treatment with JAK inhibitors is prohibited
 
	
 
• Treatment with JAK inhibitors is prohibited
 
	
 
• JAK inhibitors are prohibited as rescue therapy
 

Other Therapies				
Oral probiotics	
 
• May be receiving oral probiotics (e.g., Culturelle, S. boulardii) if dose has been stable for at least 2 weeks at the time of screening endoscopy
 
	
 
• Initiation of oral probiotics is not permitted
 
• Baseline usage of oral probiotics must remain stable during the study
 
	—	—

ATE = active treatment extension; JAK = Janus kinase; TNF = tumor necrosis factor.

a See inclusion and exclusion criteria in Section 4.1.1 and Section 4.1.2 for additional details.

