### **4.6 TREATMENT, PATIENT, STUDY, AND SITE DISCONTINUATION**

#### **4.6.1 Study Treatment Discontinuation**

Patients must permanently discontinue study treatment if any of the following criteria are met:

- Any medical condition that the investigator or Sponsor determines may jeopardize the patient's safety if he or she continues to receive study treatment
- Investigator or Sponsor determination that treatment discontinuation is in the best interest of the patient
- Confirmed anaphylaxis *related* to study treatment
- Pregnancy
- Use of a prohibited therapy, *including rescue therapy for worsening UC* (see Section 4.4.1 and Section 4.4.2)

- Significant laboratory abnormalities, confirmed on repeat laboratory collection and, *if applicable, confirmed after holding or discontinuation of concomitant medications with known relevant toxicities (e.g., latent TB infection treatments), and determined to be related to study drug:*
  - ALT, AST, or ALP  $>2.5 \times \text{ULN}$ , total bilirubin  $>2 \times \text{ULN}$ , or presence of abnormalities in synthetic liver function tests judged to be clinically significant by the investigator
  - ANC  $<1.5 \times 10^9/\text{L}$  ( $1500/\mu\text{L}$ ), with one exception:  
Patients with BEN: ANC  $<1.3 \times 10^9/\text{L}$  ( $1300/\mu\text{L}$ )
  - Absolute lymphocyte count  $<0.5 \times 10^9/\text{L}$  ( $500/\mu\text{L}$ )

*For cases of active TB or reactivation of TB, permanent discontinuation should be considered.*

The primary reason for study treatment discontinuation should be documented on the appropriate eCRF. Patients who discontinue study treatment will not be replaced.

Patients will return to the clinic for a treatment discontinuation visit within 14 ( $\pm 3$ ) days after the final dose of study treatment.

Refer to the schedule of activities (see [Appendix 1](#) and [Appendix 2](#)) for details on follow-up assessments to be performed for patients who permanently discontinue study treatment. If a patient requests to be withdrawn from treatment or follow-up assessments, this request must be documented in the source documents and signed by the investigator.

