### Investigational and Non-Investigational Medicinal Product Designations (for Use in European Economic Area and United Kingdom)

**Table 1 Investigational, Authorized Auxiliary, and Unauthorized Auxiliary Medicinal Product Designations for European Economic Area**

Product Name	IMP/AxMP Designation	Marketing Authorization Status in EEA	Used within Marketing Authorization
Vixarelimab (RO7622888)	IMP (test product)	Not approved	Not applicable
Vixarelimab placebo	IMP (placebo)	Not approved	Not applicable
Topical 5-ASA	AxMP (rescue therapy)	Approved	Yes
Oral 5-ASA	AxMP (other a )	Approved	Yes
IV corticosteroids and rectal corticosteroids (i.e., enemas or suppositories)	AxMP (rescue therapy)	Approved	Yes
Oral corticosteroids	AxMP (other a )	Approved	Yes
AZA	AxMP (other a )	Approved	Yes
6-MP	AxMP (other a )	Approved	Yes
MTX	AxMP (other a )	Approved	Yes

5-ASA=5-aminosalicylic acid; 6-MP=6-mercaptopurine; AxMP=auxiliary medicinal product; AZA=azathioprine; EEA=European Economic Area; IMP=investigational medicinal product; MTX=methotrexate.

a Used as a background or rescue therapy; will differ patient to patient.

**Appendix 6: Investigational Medicinal Product and Non-Investigational Medicinal Product Designations (for Use in European Economic Area and United Kingdom)**

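### Table 2 carries its UC therapy prohibitions into safety follow-up with no exemption for patients stopped for needing that therapy, and the rules on topical 5-ASA rescue do not agree with each other

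*Combined protocol and SAP*

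**What the plan says.** **Table 2 (Section 4.4.1).** The table has separate columns for the time before screening endoscopy and for screening plus induction, but a single column, "During Optional ATE and Safety Follow-Up", for the active treatment extension (ATE) and everything after it. A further column covers rescue therapy. Entries in the shared column include:

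- advanced therapies: "Treatment with advanced therapy is prohibited"
- JAK inhibitors: "Treatment with JAK inhibitors is prohibited"
- oral corticosteroids: "Initiation or increase in dose of oral corticosteroids above baseline steroid level is prohibited"
- IV and rectal corticosteroids: prohibited
- oral 5-ASA, and AZA, 6-MP or MTX: starting or increasing is prohibited
- topical 5-ASA: intermittent use is permitted, for up to 2 weeks of daily use, with a redacted date by which it must end.

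For topical 5-ASA the rescue column adds: "Initiation of topical (rectal) 5-ASA is considered rescue therapy and is permitted only during the optional ATE period".

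**Section 4.4.** A patient who requires a prohibited therapy "will be discontinued from study treatment (see Section 4.6.1) and will undergo follow-up assessments".

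**Section 4.6.1.** The reasons for permanent discontinuation of study treatment include "Use of a prohibited therapy", which the same bullet extends to rescue for worsening UC, with a cross-reference to Sections 4.4.1 and 4.4.2.

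**Section 9.2.** Prospective requests to deviate from the protocol are not allowed.

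**The concern.** A patient whose colitis worsens enough to need, for example, an advanced therapy is taken off study drug for that reason and passes into safety follow-up. The column that governs safety follow-up still prohibits the therapy. A site that applies the table to the letter would either not give the treatment or have to record its use as a departure from protocol, and it cannot settle the question beforehand. That touches patient safety, because the rule as written bears on the care of patients who are doing badly after study drug has stopped. It also touches the deviation record, since Section 6.2 has major deviations listed and weighed for their effect on interpretation.

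The second problem concerns the rule for stopping study drug during the ATE. If rescue for worsening UC always ends study treatment, a patient who starts topical 5-ASA in the ATE must stop. If Table 2's permission governs, the patient continues. The two places should give one answer.

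**Working it through.** No arithmetic applies; the check sets the provisions side by side.

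**A. Prohibitions after study treatment has stopped**

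1. *Which period does the column cover?* Its heading names safety follow-up. The table's footnotes deal with eligibility cross-references, budesonide and beclomethasone, and re-tapering of corticosteroids. None exempts a patient who is off study drug.
2. *Who enters that period?* Section 3.1.1 and the treatment discontinuation footnotes in Appendices 1 and 2 send patients who stop early to a discontinuation visit and then into safety follow-up. Section 4.4 says the same of patients who require a prohibited therapy.
3. *What is the trigger?* Section 4.4 acts when a prohibited therapy is required, Section 4.6.1 when it is used. Under the Section 4.4 wording the patient may be stopped before the therapy begins, so its first use can fall in the period where the table prohibits it.
4. *Does another section lift the ban?* No. Section 4.4.2.2 adds a general ban, during the study, on UC treatments not listed in Section 4.4.1. Sections 4.4 and 4.6.1 give the consequence of prohibited therapy, which is stopping study drug, and do not say that the therapy becomes allowed afterwards.
5. *Does the protocol foresee such use?* Yes. The unscheduled-visit footnotes in Appendices 1 and 2 provide optional assessments for patients who receive rescue therapy.
6. *Can a site clear it in advance?* Section 9.2 rules out prospective deviations.

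Steps 1 to 4 together mean that the same therapy is the reason for leaving study drug and remains prohibited once study drug is gone. Taken literally, the column also binds patients who completed treatment as planned and are in safety follow-up.

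**B. Topical 5-ASA**

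| Place | Rule for topical 5-ASA |
|---|---|
| Table 2, shared ATE and safety follow-up column | intermittent use permitted, within a time limit |
| Table 2, rescue column | starting it is rescue; permitted in the ATE only |
| Section 4.6.1 | rescue for worsening UC is worded as a kind of prohibited therapy; permanent stop |

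Rows 1 and 2 differ on safety follow-up. Rows 2 and 3 differ on whether starting topical 5-ASA as rescue in the ATE ends study treatment.

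**The case against.** The strongest reply is that Sections 4.4 and 4.6.1 do not contradict Table 2. They presuppose its prohibitions and attach one consequence, loss of study drug. Once that has happened no further sanction is stated, so the protocol is merely silent on whether the ban continues. This is partly right: neither section expressly permits the therapy in follow-up, so no stated permission is being overridden. But the table is not silent. It names safety follow-up and prohibits the therapies there.

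On topical 5-ASA, the head term in Section 4.6.1 is prohibited therapy, with a reference back to Table 2, so permitted rescue can plausibly be read as outside the trigger. That reading is reasonable, but the text leaves it to the reader. The redacted stop date in the shared column might also confine use to the ATE, which would narrow the conflict within the row.

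A reader might go further than the documents allow in four ways:

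- *That patients must either breach the protocol or leave follow-up.* Section 4.4 keeps them in follow-up. Section 4.6.2 lists non-compliance only as a possible reason for study discontinuation and does not name prohibited therapy.
- *That safety data will be lost selectively, or that discontinuation will differ by site.* No section makes withdrawal follow from rescue use. Adverse event reporting runs for a fixed, redacted time after the final dose (Section 5.3.1), with no cut-off at new UC therapy.
- *That all rescue is prohibited.* Topical 5-ASA in the ATE is an exception.
- *That Appendix 6 contradicts Table 2 by labelling IV and rectal corticosteroids* "AxMP (rescue therapy"). Those are regulatory product designations, not permissions, and Table 2 itself classes these drugs as rescue while prohibiting them.

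**Conclusion.** The point holds as an unreconciled conflict in the current text, in two parts. First, Table 2's prohibitions extend into safety follow-up without exempting patients who were permanently stopped for needing the prohibited therapy, so such therapy is literally a continuing departure from protocol. Second, Section 4.6.1 and the topical 5-ASA row do not clearly agree on whether that rescue ends study treatment, and the row's columns differ on safety follow-up.

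The first part rests on reading the column heading as written and on there being no exemption elsewhere in the text available. The second is weaker, because Section 4.6.1 can be read as limited to prohibited rescue and one date in the row is redacted.

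Its size cannot be put as a number of patients: any count would need an assumed rate of stopping for worsening UC, and the length of safety follow-up is redacted. The Week 12 primary analysis is not shown to be affected. Because a written rule bears on the care of patients whose disease has worsened, and the remedy is cheap, it should be corrected.

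**What to change.** Reconcile Table 2 with Sections 4.4 and 4.6.1:

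1. Give safety follow-up its own column in Table 2, separate from the ATE.
2. For each therapy row, state whether the prohibition applies after permanent discontinuation of study treatment.
3. Word the Section 4.6.1 trigger so that its relation to the topical 5-ASA rescue that Table 2 permits in the ATE is explicit.
4. Make the shared-column and rescue-column entries for topical 5-ASA say the same thing about safety follow-up.

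Which therapies are allowed, and when, is for the sponsor to decide; the request is only that the provisions agree. The cost is amendment wording in one table and in whichever of the two sections needs it, with no change to sample size, endpoints or the statistical analysis.

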#### **4.4.2        Other Concomitant Therapy**

##### **4.4.2.1        Other Permitted Concomitant Therapy**

Patients are permitted to use the following therapies during the study:

- Oral contraceptives with a failure rate of < 1% per year (see Section 4.1.1)
- Hormone-replacement therapy
- *Latent TB treatment per local standard of care, as described in Section 4.1.2*

In general, investigators should manage a patient's care with supportive therapies as clinically indicated, per local standard practice. Premedication with antihistamines, anti-pyretics, and/or analgesics may be administered at the discretion of the investigator.

Patients may continue on stable regimens of drugs they are receiving as treatment for coexistent stable diseases (e.g., antihypertensives, cholesterol-lowering drugs, or bronchodilators).

Over-the-counter preparations deemed *necessary after taking into consideration prohibited concomitant therapies, as described in Section 4.4.2.2 and not expected to interfere with the study drug*, will be allowed during the study. Initiation of over-the-counter medications during the study will need to be approved by the investigator *in consultation with the Medical Monitor, if necessary*.

##### **4.4.2.2        Other Prohibited Concomitant Therapy**

Use of the following concomitant therapies during the study is prohibited as described below:

- Any treatment for UC other than those listed in Section 4.4.1
- Chronic use of NSAIDs is prohibited prior to and during the study.  
Occasional use of NSAIDs (e.g., headache, arthritis, myalgias, or menstrual cramps), and aspirin (up to 325 mg daily) is permitted.
- Apheresis (e.g., Adacolumn® apheresis) is prohibited within 2 weeks prior to screening *endoscopy* and during the study.
- Chronic use of anti-diarrheals (e.g., loperamide, diphenoxylate with atropine) is prohibited prior to and during the study.
- *Investigational biologic and non-biologic therapy use is prohibited within 8 weeks or 4 weeks, respectively, or 5 half-lives (whichever is greater) prior to screening and during the study.*
- *Live-attenuated vaccines are prohibited within 4 weeks prior to screening and during the study.*
- *Treatment with immunoglobulin or blood products within 4 weeks prior to screening and during the study.*

## 4.5 STUDY ASSESSMENTS

The schedule of activities to be performed during the study is provided in [Appendix 1](#) and [Appendix 2](#). All activities should be performed and documented for each patient.

Patients will be closely monitored for safety and tolerability throughout the study. Patients should be assessed for toxicity prior to each dose; dosing will occur only if the clinical assessment and *recent* laboratory test values, *if available*, are acceptable.

### 4.5.1 Informed Consent Forms and Screening Records

Written informed consent for participation in the study must be obtained before performing any study-related procedures (including screening evaluations). Informed Consent Forms for enrolled patients and for patients who are not subsequently enrolled will be maintained at the study site.

All screening evaluations must be completed and reviewed to confirm that patients meet all eligibility criteria before enrollment. The investigator will maintain a detailed record of all patients screened, to document eligibility or record reasons for screening failure, as applicable.

### 4.5.2 Medical History, Baseline Conditions, Concomitant Medication, and Demographic Data

Medical history and baseline conditions, including clinically significant diseases, surgeries, cancer history (including prior cancer therapies and procedures), reproductive status, smoking history, and use of alcohol and drugs of abuse, will be recorded at screening. In addition, all concomitant therapy (see [Section 4.4](#)) used by the patient from the start of the screening period will be recorded. Demographic data, including age, sex, and self-reported race or ethnicity, will also be recorded.

A UC-specific history including complications and surgeries related to UC, and a detailed history of UC medications used by the patient within 1 year prior to the screening visit will be recorded. In addition, a detailed history of advanced therapies used by the patient within 5 years prior to the screening visit (e.g., name and duration of previous biologic therapies and reason for discontinuation) will be recorded.

The extent and duration of the patient's disease, as recorded in the patient's medical record, will be captured in the eCRF. The extent of disease should be identified as one of the following:

- Left-sided colitis (inflammation up to the splenic flexure)
- Extensive colitis (inflammation beyond the splenic flexure but not involving the entire colon)
- Pancolitis (inflammation of the entire colon)

An interval medical history should be obtained at subsequent clinic visits, and any changes in medications and allergies should be recorded.

